adaptations due to reduced iron efflux during overtraining to aid in the maintenance of physical performance has not been explored.

B3. MILITARY RELEVANCE

This study supports the Military Operational Medicine Research Program's Physiological Health and Performance Program Area under the BPE Work Unit. The BPE Work Unit is intent is to execute basic and applied research aimed at identifying and develop biomedical strategies and solutions that safely and ethically enhance Warfighter physical, cognitive, sensory and behavioral performance in training and operational environments, enabling lethality and overmatch. The proposed work aligns to the Physiological Health and Performance Strategic Plan Technical Challenge 1.1.1.1: Identify pharmacological enhancement protocols improving specific task performance under operational stress.

B4. OBJECTIVES/SPECIFIC AIMS/RESEARCH QUESTIONS

Objective

1. Determine the effects of EPO on hematological adaptions compared to baseline during 4 weeks of overtraining.
2. Determine the time course change in physical performance (time trial) with EPO compared to baseline.
3. Assess the influence of EPO non-hematological adaptation (whole-body and skeletal muscle substrate oxidation and glucose turnover) following 4 weeks of overtraining compared to baseline.

Hypothesis

1. Hemoglobin and hematocrit will be maintained with EPO during 4 weeks of overtraining.
2. Physical performance will be maintained with EPO during 4 weeks of overtraining.
3. EPO will increase whole body and skeletal muscle fat oxidation, and reduce reliance on endogenous glucose store following 4 weeks of physical training.

B5. RESEARCH PLAN

B5.1 Research Design

This study will be a longitudinal trial.

B5.2 Research Subjects/Population(s)

B5.2.1 Subject Population(s)

Subject population will be military or civilians representative of active duty male and female service members, being in good health and recreationally active.

B5.2.2 Number of Subjects, Records, and/or Specimens

A total of 8 volunteers will be required to achieve sufficient statistical power. To complete testing on 8 volunteers, we estimate we will need to enroll 60 individuals. All screening will stop once complete data has been collected on 8 volunteers. Records and specimen collection are described in the Research Procedures and Data Collection sections. During briefings and consenting potential participants will be informed that even though they may be eligible and want

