to participate, if we are able to obtain enough data from preceding subjects, they may not ultimately be tested. These individuals may be recruited from the HRV population, civilians, and active duty military personnel (on the installation).

B5.2.3 Inclusion Criteria

- Men and women aged 18 – 39 years
- Weight stable (± 5 lbs) for at least 2 months prior to the start of the study
- Body mass index (BMI) between 18.5-30 kg/m²
- Recreationally active (minimum 2-4 days per week aerobic and/or resistance exercise)
- Refrain from taking any NSAIDS (i.e., aspirin, Advil®, Aleve®, Naprosyn®, or any aspirin-containing product for 10 days before and at least 5 days AFTER each muscle biopsy. (*Tylenol® or acetaminophen is ok to use if needed for discomfort)
- Refrain from the use of alcohol and nicotine while on study diets
- Supervisor approval for federal civilian employees working within the US Army Natick Soldier Systems Center

B5.2.4 Exclusion Criteria

- Metabolic or cardiovascular abnormalities, gastrointestinal disorders (i.e., kidney disease, diabetes, cardiovascular disease, hypertension etc.)
- Personnel or family history of blood clots
- Disease or medication (i.e., diabetes medications, statins, corticosteroids, etc) that affects macronutrient utilization and/or the ability to participate in strenuous exercise
- Allergies or intolerance to foods (including but not limited to lactose intolerance/milk allergy), vegetarian practices, or medications (including, but not limited to, lidocaine (or similar) to be utilized in the study)
- History of inflammatory bowel disease
- History of seizures
- Anemia (HCT < 38) and Sickle Cell Anemia/Trait
- Abnormal PT/PTT test or problems with blood clotting
- Present condition of alcoholism, use of nutritional/sports supplements, anabolic steroids, or other substance abuse issues
- History of malignancy
- Use of oral contraceptives or hormone replacement therapy due to increased risk of clotting
- Musculoskeletal injuries that compromise the ability to exercise
- Blood donation within 8 weeks of beginning the study
- Are unwilling or unable to eat study diets and foods provided and/or follow exercise prescriptions
- Pregnancy, post-partum status, or breastfeeding

[figure not shown]
B5.3 Research Procedures

Research procedures conducted by investigators and support personnel will be in accordance with the Delegation of Authority (DOA) Log for Key Research Personnel.

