Erythropoietin Injections (Credentialled procedure): A dose (50 IU/kg body mass) of recombinant human EPO (PROCRIT, EPOETIN ALFA, Janssen Products, LP, Titusville, NJ, USA) will be injected subcutaneously 3 times per week for 4 week. Injections will be performed by credentialled study staff at USARIEM. The Office of Medical Support and Oversight (OMSO) will be the prescriber of prescription drugs used in this protocol, to include EPO. The dosing amount and frequency is on-label dosing equivalent to pediatric dosing. This dose and duration has previously been shown to be sufficient to result in hematological adaptions and increase physical performance (18, 19, 33). Hematocrit and hemoglobin will be checked weekly to ensure values remain $< 50\%$. If Hct increases above 50%, EPO injections will be stopped and Hct will be reassessed within 3 days. If hemoglobin increases more than 1 g/dL over a 1 week period EPO injections will be stopped and hemoglobin will be reassessed within 3 days. Reticulocyte count will also be assessed on the first injection day, then again during week 2 and 4 of the injection phase. Additionally, before starting prescribed exercise, volunteers will complete a short clinically relevant health questionnaire and have vital signs checked (blood pressure, heart rate, and SpO_2) which will take about 5 minutes by study staff. Copies of all health related information will be provided to the OMSO daily for review and tracking. After the final injection volunteers will continue to be

monitored for 2 weeks by participating in weekly blood draws and daily monitoring of vital signs and health questionnaire which will continue to be reviewed by OMSO. Study personnel conducting this procedure will be credentialed and listed on the DOA log with code "F."

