Volunteers will be medically cleared by the OMSO before participation in accordance with USARIEM procedures outlined for screening volunteers for research involving exercise, tracer infusions, muscle biopsies and EPO use at USARIEM. In addition, volunteers will be screened for problems with blood clotting, including prothrombin time (PT)/ partial thromboplastin time (PTT), which is a specific criterion for research involving muscle biopsies. Health problems identified during the screening process will be documented and a copy provided to the volunteer. The volunteer will be encouraged to make an appointment with their primary care provider for a full evaluation of the problem. Volunteers with evidence of any physical, mental, and/or medical conditions that would make the proposed studies relatively more hazardous will be excluded. Any personal health information collected during this screening process will be destroyed at the time of study withdrawal or at the completion of the study.

All volunteers must be willing to consume only food and beverages provided by study staff during the entire study. Additionally, volunteers must be willing to refrain from any additional exercise during the study.

C1.4 Consent Process

Informed consent documents will be provided to each prospective volunteer. Additionally, an oral presentation will be provided to prospective volunteers by the principal investigator or his designee. In case of COVID risk mitigation plans, briefings can be done virtually and consent forms can be emailed and digitally signed. The purpose of this study, procedures involved, risks, and expectations of volunteers will be explained. The principal investigator or designee will answer all group and private

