Volunteers will be allowed to withdraw at any time without penalty or loss of benefits to which they would otherwise be entitled. They will do so by informing the PI, AI or a staff member of their intent to withdraw verbally or in writing (electronic or paper/pencil). They will then be asked to verbally discuss their choice to withdraw with the PI so that reasons for withdrawal can be documented. An investigator may stop an individual's participation in the study if the volunteer is unwilling or unable to complete study procedures. An investigator may also withdraw a volunteer if the individual becomes ill or injured or it would not be in the volunteer's best interest to continue. If the participant is withdrawn by the investigator or decides to

voluntarily withdraw him/herself, all further data collection will discontinue. Any samples or data collected prior to withdrawal will be maintained. Participants will be compensated for any blood draws they completed up until that point, and they will be asked to return any remaining food items that were provided, in addition to any wrappers and diet/activity logs that they had completed up to the point of withdrawal.

C4. PRIVACY FOR SUBJECTS

To protect the volunteer's privacy, all of their research-related records will be labeled or "coded" with an assigned research volunteer number that will not include their name or any other form of identifiable information. The principal investigator or project coordinator will keep the link between volunteer number and the volunteer's research records in a locked cabinet. Any documents that will require the volunteer's name, such as the consent form, will be kept in a locked cabinet separate from any research documents that contain the volunteer's ID number. The principal investigator and project coordinator are the only people who will be able to match the research volunteer number with any of their personal identifying information.

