Measures to Minimize Risks of Harm: To minimize side effects the study will use a low dose EPO injection equivalent to a pediatric dose. Before participants begin the prescribed exercise they will complete a short clinically relevant health questionnaire (**Appendix A**) and have their vital signs (blood pressure, heart rate, and SpO₂) assessed by study staff. Copies of all health related information will be provided to OMSO daily for review and tracking. Hemoglobin and Hct values will be measured weekly during EPO injections. To minimize risk of blood clots Hct values will be maintained < 50%. If Hct values increase > 50% EPO injections will be stopped. Volunteer will return to for another Hct check within 3 days. If hemoglobin increases more than 1 g/dL over a 1 week period EPO injections will be stopped and hemoglobin will be reassessed within 3 days. EPO injections will only be administered by credentialed staff at USARIEM. These individuals will follow administration procedures provided in the PROCRIT® prescriber information guide. Volunteers will continued to be monitored for 2 weeks after the injections are complete to ensure there are no complications from the EPO injections. The OMSO will be responsible for observing and monitoring adverse events of participants in this study.

Research Procedure Name: Exercise

Research Procedure Description: Exercise testing will occur on a cycle ergometer or treadmill. Exercise will be at various levels of intensity based on exercise protocol.

Research-related Risks: Exercise per se rarely provokes cardiovascular events in healthy individuals with normal cardiovascular systems. The prevalence of fatal events in the U.S. is approximately 1:133,000 to 1: 185,000 for men and 1:769,000 to 1:1,500,000 for women who are competitive high school and college athletes. For middle-aged and older adults the relative risk rises to 1:15,000 to 1:18,000 for individuals without a prior history of cardiovascular events. Current civilian and military guidelines state that individuals less than 40 years of age who have no symptoms of or known presence of heart disease or major coronary risk factors have a low risk for cardiac

complications during vigorous exercise. All volunteers in this study fall into this low risk category. Local muscle discomfort and fatigue may occur in active muscles during and shortly after exercise. Muscle soreness, ranging in intensity from mild to severe, may persist for 1 to 7 days.

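### The entry criteria set a hematocrit floor of 38 but no numeric upper limit, although EPO is stopped above 50% to limit clot risk

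*Protocol*

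**What the plan says.** **Entry.** Protocol B5.2.4 excludes "Anemia (HCT < 38) and Sickle Cell Anemia/Trait". No other inclusion or exclusion criterion in B5.2.3 or B5.2.4 gives a number for Hct or hemoglobin. Related exclusions cover clot history, abnormal PT/PTT, hypertension and oral contraceptives.

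**On treatment.** B5.3 (Erythropoietin Injections) states: "If Hct increases above 50%, EPO injections will be stopped and Hct will be reassessed within 3 days". C6.1 (Exogenous EPO) gives the reason: "To minimize risk of blood clots Hct values will be maintained < 50" per cent. Both sections add a second stop: "If hemoglobin increases more than 1 g/dL over a 1 week period EPO injections will be stopped".

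**Clearance.** C1.3 has the medical office clear volunteers under local procedures for "screening volunteers for research involving exercise, tracer infusions, muscle biopsies and EPO use at USARIEM". It also excludes conditions that would raise the hazard. No Hct figure is given there.

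**Expected change.** B5.8.1, Table 4 (Table 1 in the SAP) includes an Hct rise of 5.1 ± 3. Hypothesis 1 in B4 expects something else: "Hemoglobin and hematocrit will be maintained with EPO during 4 weeks of overtraining".

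**Replacement.** B5.2.2 says "All screening will stop once complete data has been collected on 8 volunteers". C3 says "An investigator may also withdraw a volunteer if the individual becomes ill or injured".

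**The concern.** The hazard that the plan names for this drug is a high Hct, but its only numeric entry limit guards the low end. Someone at 48 or 49% meets every numeric criterion and sits one or two points below the level at which the plan stops dosing. C6.3 says that participants get no direct benefit, so exposure that a value already in hand could prevent is hard to justify. The second stop does not fill the gap, because it acts on the weekly rate of hemoglobin rise and not on the level.

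There is also a smaller practical cost. A volunteer whose injections are stopped has had an incomplete course, and neither B5.2.2 nor C3 says whether that person restarts, is withdrawn or is replaced.

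**Working it through.** **1. The plan's own Hct figure.** Table 4 gives effect size 1.56 and a sample size of 7. A paired t-test at two-sided 0.05 has power 86% with n = 6 and 93% with n = 7, so 7 reproduces at a 90% target (the documents state no power). The printed change gives 5.1/3 = 1.70 rather than 1.56. That is a separate matter and nothing below depends on it.

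**2. Chance of crossing 50% from a given entry value b.** Assumptions: ± 3 is the SD of individual change, changes are normal and independent of b, and a share f of each volunteer's 28-day change has occurred by day 21 (f = 0.75 if linear).

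P = 1 − Φ(((50 − b)/f − m)/3), where m is the mean rise.

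Example with b = 47, f = 0.75, m = 5.1: (4 − 5.1)/3 = −0.37, giving 64%.

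| Mean rise m | Entry 47 | Entry 49 |
|---|---|---|
| 5.1 (Table 4) | 64% | 90% |
| 2.55 (half) | 31% | 66% |
| 0 (Hypothesis 1) | 9% | 33% |

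The documents give no Hct time course. At m = 5.1, f = 0.5 gives 38% at entry 47 and 85% at entry 49; f = 1 gives 76% and 91%.

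**3. How many enter that high.** Assumed entry distribution: mean 42.8 (placebo, energy balance, in B2 Table 1) and SD 2.5 (not in the documents), cut off at the floor of 38.

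- Above 47: 1 − Φ(4.2/2.5) = 4.65%. Below 38: Φ(−4.8/2.5) = 2.74%. Share of eligible entrants above 47: 4.65/97.26 = 4.8%.
- Among 8: 8 × 0.048 = 0.38 expected. At least one: 1 − (1 − 0.048)^8 = 32%.
- SD 2 or 3: share 1.8% or 8.5%; at least one of 8, 14% or 51%.
- Mean 41.5 or 43.6 (the range of means in B2 Table 1) with SD 2.5: share 1.5% or 8.8%.
- At or above 50 at entry: under 1% for mean 42.8 and SD 2 to 3.

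**4. What a cap at 47 would change.** Simulation of 8 million draws with the step 3 distribution (SD 2.5) and step 2 changes (f = 0.75). Avoided crossings are 8 × (no cap − cap), from unrounded rates.

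| Mean rise | Crossing, no cap | Crossing, cap 47 | Avoided among 8 | Crossings from entry ≤ 47 |
|---|---|---|---|---|
| 5.1 | 16.2% | 13.2% | 0.25 | 77% |
| 2.55 | 6.0% | 3.8% | 0.17 | 61% |
| 0 | 1.7% | 0.7% | 0.08 | 41% |

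**5. Would the hemoglobin stop catch a high entrant?** B2 Table 1 gives 42.8/14.4 = 2.97 Hct points per g/dL. A linear 5.1-point rise is 5.1/2.97/4 = 0.43 g/dL per week. Exceeding 1 g/dL per week needs a rise above 4 × 2.97 = 11.9 points: 1 − Φ((11.9 − 5.1)/3) = 1.2%. This ignores measurement noise and non-linear rises.

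**6. Is there a pre-dose Hct?** Yes. B5.3 takes a venous Hct at each CO-rebreathing test, two of which precede the first dose. B5.3 also schedules a reticulocyte count on the first injection day. The blood-draw tally is 8 × 2 = 16 tracer samples + 4 CO-rebreathing + 6 safety = 26, exactly the stated total. That leaves no separate draw for the first-day count, so one of the four weekly safety draws probably falls on that day.

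**The case against.** The case against is substantial, and much of it stands.

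- **The ceiling protects everyone equally.** High entrants are stopped at the same 50%, only sooner. This is true, and it is why the point is minor. It does not explain why someone one point below the ceiling should be dosed at all.
- **Clearance may already filter high values.** The medical office sees the screening Hct and must exclude anyone for whom the study is more hazardous. C6.1 also binds staff to the manufacturer's administration guide. Either source may hold a limit, but neither is visible, so the claim concerns the written criteria only. The plan did write a number for anemia.
- **The cap is a judgement.** Nothing in the documents dictates 47. At the full planning rise, 77% of crossings come from entrants at or below it.
- **The inputs are assumed.** The entry mean comes from another study, the SD from no document, and the full rise runs against Hypothesis 1.

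A reader might infer that no pre-dose check exists. The documents do not support that: CO rebreathing measures Hct before dosing, and the draw tally suggests a first-injection-day sample. They do not say whether that result is back before the injection, and the timeline figure is not shown. For the same reason, the exact days of the weekly checks are uncertain.

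A reader might also infer that high entrants come to light only after biopsies and doses. That is wrong, since the floor requires an Hct at screening. Only an actual crossing is learned later.

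**Conclusion.** The point holds as a minor gap in the written criteria. B5.2.4 has a floor and no ceiling, the treatment rule has a ceiling justified by clot risk, and no written entry criterion acts on a high screening value that is already known.

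For an individual in the high 40s the chance of reaching the stop is material: 9% to 64% at entry 47 and 33% to 90% at entry 49, from no mean rise to the full planning rise, with a linear course to day 21. For the trial it is small, because few entrants start that high and the cap avoids only a fraction of one crossing among 8. All of these figures rest on the assumed entry distribution, normal changes and the assumed time course.

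Two stronger conclusions are not supported. The plan does not license dosing at or above 50%, because C6.1 already implies a start below it. Nor is the sample of 8 endangered: screening continues until 8 have complete data and investigators may withdraw volunteers, so replacement is possible although no rule spells it out.

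**What to change.** 1. **B5.2.4:** add an exclusion for screening Hct above a stated cap set by the medical office. 47% is a reasonable starting proposal, and the office may choose lower.
2. **B5.3:** state that the first injection is withheld if the latest pre-dose Hct (CO-rebreathing or first-injection-day draw) is at or above 50%. This makes explicit what C6.1 implies.

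**Cost.** The cap uses an Hct already needed for the floor, and the hold uses a sample already drawn. At 47, expect about 5% more screen failures (1.8% to 8.5% for SD 2 to 3 at mean 42.8). That is about 60 × 0.048 = 3 people if all 60 planned enrolments otherwise met the floor. The study population becomes slightly narrower. A volunteer who fails only the first-dose hold would already have had the three baseline biopsies, but this should be rare.

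**Limit.** The cap helps only the highest entrants. It does not replace a rule on whether a stopped volunteer restarts, is withdrawn or is replaced.

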Negative hematological adaptations due to prolonged periods of strenuous physical activity may, in part, contribute to declines in physical performance during military operations. Exogenous erythropoietin (EPO) is a potential intervention that may be used to maintain hemoglobin (hgb), hematocrit (Hct), and physical performance during periods of high physical activity. The objective of the current study is to determine the ability of EPO to maintain hgb, Hct, and physical performance compared to baseline measures. Additionally, EPO may result in non-hematological adaptations which increase mitochondria biogenesis and alter substrate oxidation. As such, this study will also assess the influence of EPO on whole-body and skeletal muscle substrate oxidation. Eight healthy physically active individuals will be recruited to participate in this longitudinal trial. After exercise practice sessions, volunteers will complete baseline physical performance (time trial) and substrate oxidation testing. Participants will then receive EPO injections 3 times per week for 4 weeks. Diet and exercise will be controlled during the injection period. Participants will undergo four weeks of an intense physical training exercise program. Every seventh day during the injection period a safety blood sample, assessing hematocrit, will be drawn, and participants will complete a 5 km time trial to determine the time course of changes in physical performance can be detected. After the 4 weeks of EPO injections volunteers will complete the same physical performance and substrate oxidation testing. Substrate oxidation will be assessed during 90-min steady-state load carriage (30% body mass) exercise on a treadmill at $55 \pm 5\%$ of $\text{VO}_{2\text{peak}}$. 6-6-[²H₂] glucose tracer technique and indirect calorimetry will be used measure substrate oxidation. Muscle biopsies will be performed to measure muscle glycogen, enzyme activity, and molecular markers of metabolism and inflammation before, and immediately and 3-hrs post exercise. Multiple blood samples will be collected throughout the study to determine alterations in hemoglobin, hematocrit, and markers of substrate metabolism, and inflammation. All study procedures will occur at USARIEM. The primary risks associated with this study include those associated with EPO injection, exercise, blood draws, and muscle biopsies.

B2. BACKGROUND AND SIGNIFICANCE

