Study Design Overview: Healthy physically active individuals will be recruited to participate in this longitudinal trial. After baseline assessments of body composition, resting metabolic rate (RMR), $\text{VO}_{2\text{peak}}$ and exercise familiarization; volunteers will complete physical performance and substrate oxidation testing (Figure 3). Physical performance will be assessed using time trial. Substrate oxidation will be assessed by volunteers performing 90-min of steady-state load carriage (30% body mass) exercise on a treadmill at $55 \pm 5\%$ of their $\text{VO}_{2\text{peak}}$. 6-6-[$^2\text{H}_2$] glucose will be used as a tracer to assess glucose turnover. Indirect calorimetry will be used to determine carbohydrate and fat oxidation. Muscle biopsies will be performed to measure muscle glycogen, enzyme activity, and molecular markers of substrate metabolism before, immediately after, and 3-hrs post exercise. Multiple blood samples will be collected on substrate oxidation protocol days. To minimize carry over effects of muscle biopsies on subsequent exercise performance, volunteers will not exercise for 3 days. During the first two days of this period, volunteers will undergo carbon monoxide (CO) rebreathing to measure Hgb mass and blood volume. Volunteers will then receive EPO injections 3 times a week for 4 weeks. During the injection period all volunteers will have safety blood draws to assess Hct once a week. Volunteers will also complete a physical performance test once a week to determine time course change in performance with EPO compared to baseline. Exercise training will be controlled during the injection phase, consisting of a combination of endurance- and resistance-type exercise. During the final week of the injection phase body composition, resting metabolic rate (RMR) and $\text{VO}_{2\text{peak}}$ will be reassessed. At the end of the 4-week injection phase volunteers will complete a final physical performance test and substrate oxidation protocol, followed by two CO rebreathing tests on subsequent days. All food and beverages (except water) will be provided to volunteers beginning at the pre injection physical performance and substrate oxidation through the duration of the study. All data collection will occur at USARIEM.

Figure 3: Study Timeline

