movement once the hood is placed over their heads to collect expired air. The test will be discontinued when 20-min of steady state oxygen consumption ($\dot{V}O_2$) and carbon dioxide production ($\dot{V}CO_2$) are recorded. This measurement will be repeated during the last week of the injection phase to assess for changes in RMR. Baseline assessment of RMR, a factor of daily living, and Harris Benedict equation will be used to determine energy needs for study diets.

Study Diets (non-credentialed procedure): Registered Dietitians will develop individualized daily menus using Food Processor SQL (ESHA Research, Salem, OR, Version 10.14). The diets will be derived primarily from components of the US military Meals Ready-to-Eat (MRE) rations to achieve appropriate macronutrient proportions. Energy content of diets during glycogen normalization will match volunteers estimated energy needs to maintain body weight. Volunteers will be consuming a diet providing approximately 55% carbohydrate, 15% protein, and 30% fat. Dietary iron will be controlled for providing a minimum of 18mg/day to ensure recommended dietary allowance (RDA) for both males (8mg/day) and females (18mg/day) is met.

Time Trial (credentialed procedure): Following a 10 hr overnight fast, volunteers will complete a 5 kilometer time trial. The treadmill will be set at a constant 1% grade (36) for the entire test. Following a warm-up period, volunteers will blindly modulate treadmill speed in order to complete the distance as quickly as possible. The only feedback given will be distance covered at half mile increments. At half mile increments volunteers' rate of perceived exertion will be determined using the Borg Scale. Heart rate will be monitored throughout the time trial. Heart rate will be recorded at half mile increments. No motivation will be provided during the time trial. Participants may consume water *ad libitum* during the time trial. Following completion of the test, a self-selected cool-down will occur. Volunteers will complete a minimum of two practice exercise sessions to ensure they are familiar with the performance test. The practice sessions also will establish the coefficient of variation. Study personnel conducting maximal aerobic testing will be credentialed and listed on the DOA log with code "J."

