5.7.1.1 FDA-approved device being used in this research according to the approved labeling

DEXA, DPX-IQ, Lunar Corporation, True Max 2400, Parvomedics, Sandy, Utah, USA, Polar Electro Inc, Oulu, Finland

5.7.1.2 FDA-approved device being used in this research in a manner other than its approved labeling: N/A

B5.7.2 Drugs

B5.7.2.1 FDA-approved and used in accordance with the approved labeling

B5.7.2.2 FDA-approved and used in a manner not in accordance with its approved labeling:
PROCRIT, EPOETIN ALFA, Janssen Products, LP, Titusville, NJ, USA

B5.7.2.3 Any drug not approved by the FDA: N/A

B5.8 Statistical Analysis

B5.8.1 Sample Size Estimation

Based on results for multiple outcomes across different studies (**Table 4**) a sample size of 8 is required to statistical significance.

Table 4: Previous study effect sizes

Study	Outcome	Delta	Effect Size	Sample Size
Thomson et al. (18)	TTE	10 ± 6	1.40	7
Plenge et al. (24)	Hct	5.1 ± 3	1.56	7
Caillaud et al. (19)	CHO Oxidation	0.7 ± 0.3	1.24	4
Caillaud et al. (19)	Fat Oxidation	0.2 ± 0.05	3.51	2

B5.8.2 Data analysis

Statistical analyses will be conducted using either SPSS (IBM Corp. Armonk, NY), SAS 9.3 (SAS Institute Inc., Carey, NC), or equivalent. Common descriptive statistics will be used to describe volunteer characteristics. Shapiro-Wilk tests will be used to determine normality of data. Paired t-tests will be used to assess phase effects (PRE vs. POST injection) for glucose turnover, and substrate oxidation. Repeated measures ANOVA will be used to assess main effects of time for physical performance. Mixed-model repeated measure ANOVA will be used to assess main effects of phase (PRE vs. POST injection), time and their interaction for blood analytes and muscle molecular analysis. If interactions are significant, appropriate post-hoc correction will be used to examine these relationships. Correlation coefficients and multiple regression analysis will be used to evaluate relationships between study outcome measures. The alpha level will be adjusted for multiple comparisons, with the level for statistical significance set at $P < 0.05$.

SECTION C: HUMAN RESEARCH PROTECTIONS

C1. RECRUITMENT AND CONSENT

C1.1 Identification and Selection of Subjects

Volunteers will be recruited from the federally and non-federally employed civilian population, the Natick Human Research Volunteer (HRV) Pool, and NSSC active duty military personnel.

C1.2 Recruitment Process

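### Objective 2 is measured by a 5-km time trial, but the only performance basis for n = 8 is a TTE effect, so the power statement is unsupported for that objective

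*Protocol*

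**What the plan says.** **Endpoint.** Objective 2 (protocol B4) is to "Determine the time course change in physical performance (time trial) with EPO compared to baseline". Hypothesis 2 is that "Physical performance will be maintained with EPO during 4 weeks of overtraining". The Study Design Overview in B5.3 states: "Physical performance will be assessed using time trial". The distance is 5 km both in the abstract ("participants will complete a 5 km time trial") and in the Time Trial procedure ("volunteers will complete a 5 kilometer time trial"). That procedure fixes the distance and the treadmill grade, has volunteers finish as fast as they can, and leaves the coefficient of variation to be established from the practice sessions.

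**Data table.** In B5.4 the physical performance row gives TTE as its operational specification. Neither document defines the abbreviation. The words time to exhaustion occur only in the title of a cited reference, so that is the probable reading and no more.

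**Sample size.** B5.8.1 and the SAP open in the same way, "Based on results for multiple outcomes across different studies", and arrive at 8. Protocol Table 4 and SAP Table 1 carry the same four rows: TTE, Hct, CHO oxidation and fat oxidation. The TTE row shows a delta of 10 ± 6, effect size 1.40 and n = 7. B5.2.2 then says, with no objective named: "A total of 8 volunteers will be required to achieve sufficient statistical power".

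**Analysis.** B5.8.2 and the SAP plan a repeated measures ANOVA for the main effect of time on performance. Alpha is to be adjusted for multiple comparisons by a method that is not named.

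**The concern.** The outcome behind the sample size is not the outcome that Objective 2 measures. If TTE means time to exhaustion, a test run until the volunteer stops has been used to size a test run over a fixed distance. The two need not share a standardized effect, and the documents offer no bridge between them. If TTE means something else, an undefined term stands where 5-km completion time belongs.

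Hypothesis 2 predicts no loss of performance, so a non-significant time effect is the result most easily taken as confirmation. How much such a result says depends on how large a change in 5-km time 8 people could have revealed. The documents give no figure for this, yet they describe power as sufficient.

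**Working it through.** **1. Inputs.** From the documents: n = 8 completers, alpha 0.05, and the TTE row (effect size 1.40, n = 7). Assumed, because the documents do not state them: two-sided testing, 80% power, and a paired t-test with the effect size in SDs of within-person change.

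Power = P(|T| > t(1 − α/2, n − 1)), where T is noncentral t with n − 1 df and noncentrality d × √n.

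**2. Reproducing the TTE row.** With d = 1.40:

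- n = 6: power 0.78
- n = 7: power 0.87
- n = 8: power 0.92

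The smallest n that reaches 80% is 7, as the table prints. The row is therefore consistent with a single unadjusted paired comparison of TTE.

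**3. Does another row supply the basis for Objective 2?** The remaining rows are haematocrit and substrate oxidation, which are not performance outcomes. Taken at their stated effect sizes under the same assumptions, the four rows need n = 7 (TTE), 6 (Hct), 8 (CHO oxidation, 1.24) and 3 (fat oxidation). The largest is 8, so the headline number could come from CHO oxidation, although that row prints 4. Either way, it says nothing about 5-km time.

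**4. Power for the time trial.** It cannot be computed, because neither document gives an effect, SD or CV value for it. The size of the gap can only be shown over assumed true effects at n = 8:

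| Assumed effect (SD of change) | One comparison, α = 0.05 | Bonferroni for four, α = 0.0125 |
|---|---|---|
| 0.5 | 0.23 | 0.09 |
| 0.8 | 0.50 | 0.24 |
| 1.0 | 0.68 | 0.39 |
| 1.2 | 0.83 | 0.56 |
| 1.40 (the TTE value) | 0.92 | 0.71 |

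The division by four (0.05 / 4 = 0.0125) assumes four post-baseline trials, each compared with baseline. The plan does not name these contrasts.

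**5. Detectable change.** Solving for d at n = 8 and 80% power gives 1.16 SD at α = 0.05 and 1.53 SD at α = 0.0125.

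**6. Precision.** The 95% CI half-width for one paired change is t(0.975, 7) / √8 = 2.365 / 2.828 = 0.84 observed SDs of change. An estimate of exactly zero would then carry an interval from −0.84 to +0.84 SD. That result would be non-significant, but on its own it would not establish that performance held.

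**The case against.** **The B5.4 entry is only a label.** This largely stands. The Time Trial procedure is fully specified and no TTE test is described anywhere in B5.3. A reader might infer that it is unclear which test will be run. The documents do not support that: the variable is mislabelled in one table cell. Correcting the cell would not repair the sample-size argument, because the SAP repeats TTE as its only performance basis.

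**Borrowing an effect from a related outcome is ordinary in a small single-group study, and the plan says openly that several outcomes were used.** That is fair as a description of practice. It does not supply the missing step, since neither document says why an effect of 1.40 on TTE should hold for 5-km time.

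**Eight may well be enough.** This stands. A reader might infer that the study is underpowered for Objective 2, but the documents cannot show that. A true time-trial effect of about 1.16 SD or more would have at least 80% power in a single paired comparison. Removing the TTE row would also leave 8 as the largest n that the stated effect sizes require.

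**The plan nowhere says that a non-significant result will be read as maintenance.** Correct. Such a rule would be an inference from Hypothesis 2 and the planned test, not something written. The advice on interpretation is a safeguard and would be sensible even with a good time-trial effect size.

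**Figures tied to the planned ANOVA would need further assumptions.** They would require sphericity, a set of contrasts and a count of trials. The count is not certain from the text: the overview has weekly tests and also says "At the end of the 4-week injection phase volunteers will complete a final physical performance test and substrate oxidation protocol", without saying whether that last test is one of the weekly ones. For this reason the figures above are limited to paired comparisons and are for scale only.

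**Conclusion.** The point holds in a limited form. The performance variable in B5.4 is mislabelled, and the sufficient-power statement in B5.2.2 has no support for Objective 2, because its only performance basis is a differently named outcome with no argument for transfer. The finding does not show that 8 is too few, and it does not touch the haematological or substrate oxidation objectives.

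The mismatch and the absence of time-trial inputs are read directly from the documents and need no assumption. The size of the consequence does: under two-sided testing and 80% power, one paired comparison at n = 8 detects about 1.16 SD of change, or about 1.53 SD with an assumed Bonferroni correction for four. If the TTE effect did carry over in full, power would be 0.92 unadjusted and 0.71 adjusted. At an assumed 0.5 SD it would be 0.23 unadjusted. This should be corrected; it is not a reason to hold the trial.

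**What to change.** 1. In B5.4, replace TTE with 5-km completion time.
2. In B5.8.1 and the SAP, stop using the TTE row as support for Objective 2. Either give a sourced time-trial effect and SD, or state that n = 8 was not sized on the time trial. Qualify the sentence in B5.2.2 to match.
3. In B5.8.2 and the SAP, state that the change in 5-km time from baseline will be reported with its 95% CI, and that a non-significant main effect of time will not by itself be taken as evidence of maintained performance.

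If a detectable change is quoted, tie it to the analysis actually used and label its assumptions. The SD figures above give scale and are not proposed as protocol text.

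The cost is editing text and tables, with no added volunteers, tests or procedures. The downside is a less favourable power statement for Objective 2.
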